#### 2.4.2 Control Arm

The control arm will consist of enrolled subjects who were determined by the randomization process to receive the control treatment regimen, which consists of prompt antiplatelet medical therapy alone, with no closure of the PFO.

### 2.5 Study Endpoints

#### 2.5.1 Primary Endpoints

Co-primary Endpoint 1 is freedom from a recurrent stroke or imaging-confirmed TIA through at least 24 months post-randomization. For this study, a **recurrent stroke or imaging-confirmed TIA event** is defined as the first occurrence, post-randomization, of one of the following:

- Clinical finding of ischemic stroke that may be associated with MRI evidence of a new relevant brain infarction. For this study, an ischemic stroke is defined as a neurological deficit, presumed due to ischemia, persisting longer than 24 hours or until death.
- Clinical finding of TIA that also has MRI evidence of a new relevant brain infarction. For this study, a TIA is defined as a transient neurological deficit, presumed due to ischemia, persisting less than 24 hours.

Co-primary Endpoint 1 will be calculated as the time from randomization to the first recurrent event. Subjects free from a recurrent event will be censored at the date of last known contact.

All deaths and suspected recurrent stroke/TIA events will be reviewed and adjudicated by a Clinical Events Committee (CEC). In the event of subject death, all possible efforts will be made to obtain relevant records from the hospital or the subject's primary care physician, including a death certificate or autopsy report, to determine the cause of death.

Co-primary Endpoint 2 is the incidence of subjects with new brain infarct or stroke from screening through 24 months or last follow-up visit, whichever occurs first, hereinafter referred to as **brain infarct**. A responder is defined as any subject with at least one new T2 hyperintense MRI lesion with diameter  $\geq 3$  mm from screening or clinical findings of ischemic stroke, through 24 months or last follow-up visit, whichever occurs first. It will be calculated as a subject-based binomial proportion.

CONFIDENTIAL INFORMATION

MD133254 Statistical Analysis Plan Template

Revision#: 1

Doc Type: GC

## 2.5.2 Secondary Endpoints

**Safety Endpoints** will include the proportion of subjects who experience adverse events (AEs) that are determined to be related to device, procedure, and/or antiplatelet medical management. This will include specific adverse events and groups of adverse events such as all-cause adverse events, device-related events, procedure-related events, antiplatelet medical therapy-related events, and any serious adverse events.

The safety endpoints may also be analyzed using time-to-event methods to estimate the percentage of subjects free from the event at time points of interest, such as 30 days and 24 months post-randomization (or post-procedure for the test arm).

**Efficacy Endpoints** will evaluate the success of the device in achieving PFO closure in subjects randomized to the test arm. PFO closure success will be measured by assessing the degree of residual right-to-left shunt after device implant. Time points for the assessment of PFO closure include early post-procedure, 1 month, 12 months, and 24 months.

Additional Secondary Endpoints will include:

1. **Clinical Success** –
  - a. Test Arm – defined as the composite of Device Success, PFO closure, and absence of a recurrent stroke or imaging-confirmed TIA at 24 months post-procedure
  - b. Control Arm – defined as the freedom from a recurrent stroke or imaging-confirmed TIA at 24 months post-randomization
2. **Overall Survival** – defined as time from randomization to death from any cause or last known contact
3. **Time to any stroke/TIA** – defined as time from randomization to first occurrence of stroke or TIA
4. **Device Success** – defined as the proportion of device arm subjects with successful implant and retention of the device after procedure (test arm only)

## 2.6 Statistical Hypotheses

This study is designed to test the null hypothesis that the hazard of a recurrent stroke or imaging-confirmed TIA in subjects treated with percutaneous PFO closure plus antiplatelet medical management is equal to or higher than subjects treated with antiplatelet medical management alone. The alternative hypothesis is that the hazard of a recurrent stroke/imaging-confirmed TIA is lower in subjects treated with percutaneous PFO closure plus antiplatelet medical management compared to antiplatelet medical management alone. In statistical terms:

$$\mathbb{H}_0: HR_{T/C}(t) \geq 1.0 \text{ for all } t$$

$$\mathbb{H}_1: HR_{T/C}(t) < 1.0 \text{ for all } t$$

where  $HR_{T/C}$  is the hazard ratio comparing the test (T) arm to the control (C) arm.

In addition, this study will test the null hypothesis that the incidence of brain infarct at 24 months in subjects treated with percutaneous PFO closure plus antiplatelet medical management is equal to or higher than subjects treated with antiplatelet medical management alone. The alternative hypothesis is that the brain infarct incidence is lower in subjects treated with percutaneous PFO

CONFIDENTIAL INFORMATION

MD133254 Statistical Analysis Plan Template

Revision# 1

Doc Type: GC

closure plus antiplatelet medical management compared to antiplatelet medical management alone. In statistical terms:

$$\text{H}_0: P_C - P_T \leq 0$$

$$\text{H}_1: P_C - P_T > 0$$

where:

$P_C$  = true proportion of subjects with incident brain infarct in the control group

$P_T$  = true proportion of subjects with incident brain infarct in the test group

## 2.7 Sample Size Determination

### 2.7.1 Sample Size Assumptions

Based on literature available at the study's initiation (see Section 1.0 of the study protocol), the proportion of PFO patients free from a recurrent stroke or imaging-confirmed TIA at 24 months after initial, cryptogenic stroke or imaging-confirmed TIA is assumed to be approximately 92%, with a range of 86% to 94%. For the purposes of determining sample size for adequate power, a 55% reduction in the hazard of a recurrent stroke or imaging-confirmed TIA is considered a clinically relevant benefit.

At the time this study was designed, Co-primary Endpoint 2 was considered a secondary endpoint and was not relevant to the sample size assumptions.

### 2.7.2 Randomization and Enrollment

Subjects will be randomized in a 2:1 allocation ratio with the greater proportion of subjects randomized to the test arm. Enrollment of 120 to 140 subjects per year is anticipated, for a total enrollment period of 60-66 months (5 to 5.5 years).

[figure not shown]

CONFIDENTIAL INFORMATION

MD133254 Statistical Analysis Plan Template

Revision#: 1

Doc Type: GC

CONFIDENTIAL INFORMATION

MD133254 Statistical Analysis Plan Template

Revision# 1

Doc Type: GC

[figure not shown]
[REDACTED]

[REDACTED]

[REDACTED]

[REDACTED]

[REDACTED]

## 3.0 Study Data Collection

### 3.1 *Study Data Collection Intervals*

Refer to Section 5, Data Collection And Evaluation, in the protocol.

### 3.2 *Study Interval Windows*

For Test Arm subjects, all follow-up intervals are calculated from the day of the PFO closure procedure.

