3.7. Randomization and Enrollment

Upon completion of screening tests and confirmation of study eligibility, consented patients will be **randomized** to a treatment arm. Using the EDC database approved by the Sponsor, the patient will be assigned to a treatment arm in the study. Patients will have a 2-in-3 chance of being randomized to the test (device) arm.

Because of the inclusion criteria of prior cryptogenic stroke, patients may have already initiated antiplatelet medical therapy prior to randomization. All patients will be instructed to continue antiplatelet medical therapy or begin antiplatelet medical therapy, according to the regimen prescribed in this protocol and upon instruction of their Neurologist Investigator.

For all patients randomized, if the subject has already initiated antiplatelet medical therapy prior to randomization, treatment should continue based on the antiplatelet regimen prescribed in this protocol (see Section 3.9 – Initiation and Administration of Antiplatelet Therapy). If antiplatelet medical therapy is not in progress or a regimen change is required, treatment should commence promptly (within 48 hours of randomization).

Patients randomized to the test (device) arm must be treated (have a PFO closure attempt) **within 90 days** of randomization.

Patients are considered "**subjects**" enrolled in the study following randomization to a treatment arm. A patient is considered **enrolled** into the clinical study when:

- he/she signs the consent form, and
- he/she completes all required screening tests and evaluations, and
- he/she meets inclusion/exclusion criteria, and
- he/she is randomized to a treatment arm.

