3.13. Follow-up Time Allowances – Test Arm

Follow-up visits will be scheduled at appointed times after the date of treatment. The Sponsor recognizes that subjects may not be able to return for follow-up visits on the exact date required. Thus, periods during which each visit is allowed, (i.e., "window"), are described below (**Table 5**).

Follow-up Visit Window	Time Interval During which Visit Must Occur
Early Post- procedure	Typically 4-72 hours post PFO closure procedure, but must be completed prior to leaving the hospital , out-patient facility, or surgical-center
1 month	1 month ± 2 weeks post PFO closure procedure
6 months	6 months ± 1 month post PFO closure procedure
12 months	12 months ± 2 months post PFO closure procedure
18 months	18 months ± 2 months post PFO closure procedure
24 months	24 months ± 2 months post PFO closure procedure
Year 3	36 months ± 2 months post PFO closure procedure
Year 4	48 months ± 2 months post PFO closure procedure
Year 5	60 months ± 4 months post PFO closure procedure

Table 5. Schedule of Test Arm Subject Follow-up and Associated Visit Windows

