3.15. Follow-up Time Allowances - Control Arm

Follow-up visits will be scheduled at appointed times after the date of treatment. The Sponsor recognizes that subjects may not be able to return for follow-up visits on the exact date required. Thus, periods during which each visit is allowed, (i.e., "windows"), are described below (**Table 7**).

Follow-up Visit Window	Time Interval During which Visit Must Occur
1 month	1 month ± 2 weeks post randomization
6 months	6 months ± 1 month post randomization
12 months	12 months ± 2 months post randomization
18 months	18 months ± 2 months post randomization
24 months	24 months ± 2 months post randomization
Year 3	36 months ± 2 months post randomization
Year 4	48 months ± 2 months post randomization
Year 5	60 months ± 4 months post randomization

Table 7. Schedule of Control Arm Subject Follow-up and Visit Windows

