### 2.2 *Design Summary*

The Gore REDUCE Clinical Study is a prospective, randomized, multinational, multicenter evaluation comparing antiplatelet medical management without PFO closure (control arm) to PFO closure with the study device plus antiplatelet medical management (test arm) for the reduction of recurrent stroke or imaging-confirmed TIA or new brain infarct in subjects with a PFO and history of cryptogenic stroke or imaging-confirmed TIA.

A total of 664 eligible subjects will be randomized to either the test or control arm using a 2:1 randomization scheme. A maximum of 80 investigational sites in the United States, Canada, and Europe will participate in the study with no per-site subject limit. The anticipated accrual rate is approximately 10 subjects per month for a total accrual period of approximately 60-66 months.

Randomized subjects will be followed for up to five (5) years. For the control arm, follow-up intervals will be calculated from the date of randomization. For the test arm, follow-up intervals will be calculated from the date of the transcatheter closure procedure. All subjects will receive follow-up evaluations at 1, 6, 12, 18, 24, 36, 48, and 60 months. Test arm subjects will receive an additional follow-up evaluation at early post-procedure (within 4 to 72 hours following the transcatheter closure procedure).

CONFIDENTIAL INFORMATION

MD133254 Statistical Analysis Plan Template

Revision# 1

Doc Type: GC

3 of 17

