### 2.4 Study Treatment Arms

#### 2.4.1 Test Arm and Test Device

The test arm will consist of enrolled subjects who were determined by the randomization process to receive the test treatment regimen, which consists of prompt antiplatelet medical therapy and PFO closure with the test device within 90 days of randomization. At the start of enrollment in December 2008, the test device was the GORE® HELEX® Septal Occluder; with Protocol Amendment 2, dated May 15, 2012, the test device was changed to the GORE® CARDIOFORM Septal Occluder.

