**Schedule of Test Arm Subject Follow-up and Visit Windows**

Follow-up Visit Interval	Follow-up Visit Interval Window
Early Post-procedure	Typically 4-72 hours post-PFO closure procedure, but must be completed prior to leaving the hospital, out-patient facility, or surgical center
1 month	1 month (30 days) $\pm$ 2 weeks (14 days)
6 months	6 months (182 days) $\pm$ 1 month (30 days)
12 months	12 months (365 days) $\pm$ 2 months (60 days)
18 months	18 months (547 days) $\pm$ 2 months (60 days)
24 months	24 months (730 days) $\pm$ 2 months (60 days)
Year 3	36 months (1,095 days) $\pm$ 2 months (60 days)
Year 4	48 months (1,460 days) $\pm$ 2 months (60 days)
Year 5	60 months (1,825 days) $\pm$ 4 months (120 days)

For Control Arm subjects, all follow-up intervals are calculated from the day of randomization.

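### Endpoint 2's 24-month MRI is timed from closure in the test arm but from randomization in the control arm, and the crude proportion test ignores the difference; the bias runs against the device

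*SAP*

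**What the plan says.** SAP 3.2 sets two clocks: "For Test Arm subjects, all follow-up intervals are calculated from the day of the PFO closure procedure" and "For Control Arm subjects, all follow-up intervals are calculated from the day of randomization". SAP 2.2 and Protocol 2.2 say the same. In the protocol's visit tables the 24-month visit, which carries the MRI, is due "24 months ± 2 months post PFO closure procedure" in the test arm (3.13) and "24 months ± 2 months post randomization" in the control arm (3.15). SAP 3.2 puts both at day 730 ± 60 on their own clocks. The test regimen in SAP 2.4.1 includes "PFO closure with the test device within 90 days of randomization", and Protocol 3.7 makes the same 90-day requirement.

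Both arms are compared with a screening MRI taken before randomization (Protocol 3.5). SAP 4.3.2 divides responders by evaluable subjects and applies an unpooled z-test, with no term for time observed.

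SAP 2.5.1, 2.6 and 4.3.2 give no origin for the 24 months of Endpoint 2, whereas SAP 2.5.1 times Endpoint 1 from randomization. Table 3 in Protocol 3.12 counts visits post-procedure even for test subjects with no occluder implanted, so a test subject who never has a procedure has no stated origin.

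The text of Protocol 3.15 says of control subjects "Follow-up visits will be scheduled at appointed times after the date of treatment", while Table 7 in the same section counts from randomization.

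**The concern.** New lesions and strokes accumulate and stay counted. If one arm is observed for longer, the extra time can only add responders to it. Here the longer-observed arm is the test arm, so part of any true benefit is hidden. What is at stake is a co-primary estimate and its 95% confidence interval, plus some power. No planned output would show how large the effect was: the worst-case, best-case and tipping-point analyses in SAP 4.10 deal with withdrawal and loss to follow-up, not with MRI timing.

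**Working it through.** **No stated figure to reproduce.** The visible text gives no infarct rate, effect or power for Endpoint 2. The protocol's contents list a section on brain infarct power (2.6.4), but its text is not shown, so this is not an omission by the sponsor.

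**Inputs from the documents.** MRI at day 730 ± 60 on each clock (SAP 3.2); closure limit of 90 days (Protocol 3.7, SAP 2.4.1); 443 test and 221 control subjects (Protocol 3.3); unpooled z, one-sided 0.025 (SAP 4.3.2), taken here before multiplicity adjustment.

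**Assumed inputs.** Control proportion 10%. Hazard ratio (HR) 0.45 after closure, borrowed from the 55% reduction that SAP 2.7.1 gives for Endpoint 1. The same delay d for every test subject. All subjects evaluable. Weibull hazard shape k from 0.5 (declining) to 1 (constant). Screening MRI L days before randomization, with L from 0 to 180 because Protocol 3.5 allows screening within 180 days of the qualifying event.

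**Step 1, calendar.** The nominal test-arm MRI falls at day 730 + d after randomization, against 730 for control. At d = 90 that is 820, or 90/730 = 12.3% more time. With the windows, the ranges are 670 to 880 and 670 to 790.

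**Step 2, model.** With s in days since the screening MRI, the control cumulative hazard is Λ(s) = Λ₀·(s/(730+L))^k, where Λ₀ = −ln(0.90) = 0.10536. For the test arm,

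p_T(E) = 1 − exp{−[Λ(L+d) + 0.45·(Λ(E) − Λ(L+d))]},

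with E = L+730 if the MRI were timed from randomization, and E = L+730+d as planned. The comparison isolates the extra observation; dilution from the days before closure is present in both.

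**Step 3, one case in full (k = 1, L = 0, d = 45).**
- Λ(45) = 0.10536 × 45/730 = 0.00649, and Λ(775) = 0.10536 × 775/730 = 0.11186.
- Common clock: 0.00649 + 0.45 × (0.10536 − 0.00649) = 0.05098, so p_T = 4.97%.
- Planned: 0.00649 + 0.45 × (0.11186 − 0.00649) = 0.05391, so p_T = 5.25%.
- The difference from control falls from 5.03 to 4.75 points. The extra responders are 443 × 0.00277 = 1.2.

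**Step 4, range at d = 45.** Power is by exact binomial enumeration of the plan's z-test.

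| k | L | Difference, common → planned (points) | Extra responders of 443 | Power, common → planned | Loss (points) |
|---|---|---|---|---|---|
| 1 | 0 | 5.03 → 4.75 | 1.2 | 0.6123 → 0.5529 | 5.9 |
| 0.75 | 0 | 4.69 → 4.48 | 0.9 | 0.5392 → 0.4953 | 4.4 |
| 0.5 | 0 | 4.01 → 3.87 | 0.6 | 0.3978 → 0.3715 | 2.6 |
| 1 | 180 | 4.01 → 3.79 | 1.0 | 0.3989 → 0.3565 | 4.2 |
| 0.5 | 180 | 2.66 → 2.55 | 0.5 | 0.1808 → 0.1681 | 1.3 |

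**Step 5, other delays and evaluability (k from 1 to 0.5).** With L = 0 the loss is 1.9 to 1.0 points at 15 days and 11.6 to 4.3 points if every subject waited 90 days. With L = 180 the 90-day loss is 7.6 to 2.1. With 80% evaluable (177/354), L = 0 and 45 days it is 5.3 to 2.2.

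**Step 6, no effect (HR 1, control 10%, L = 0).** The test rejects with probability 0.020 with no delay, 0.011 to 0.015 at 45 days and 0.006 to 0.011 at 90 days. It becomes more conservative.

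**Step 7, if clinical events already stop at 24 months from randomization.** Only lesions found on MRI then carry the offset. If 25% to 50% of late events are clinical, the 45-day loss at L = 0 is 4.4 to 3.0 points (k = 1) or 2.0 to 1.3 (k = 0.5).

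**The case against.** The two clocks are stated openly and consistently, and they also serve the test arm's 24-month echocardiographic assessment of closure. The resulting bias is conservative. The size depends on four quantities that cannot be seen: delay, infarct rate, effect and hazard shape. In the illustration it amounts to about one responder among 443. SAP 4.3.2 limits confirmed recurrent events to 24 months, and the 24-month origin stated for recurrent events in Endpoint 1 is randomization. If that governs here too, only the MRI component is affected. The date-of-treatment wording in Protocol 3.15 looks like a slip, since Table 7, Protocol 2.2 and SAP 3.2 all say randomization.

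Most of this stands. It limits the weight of the point and is why the power figures are illustrations only. It does not remove the point. An openly stated visit schedule does not adjust an analysis that ignores it, and the origin for Endpoint 2 is left to the analyst.

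A reader might infer that 90 days is a hard ceiling on the extra observation. The documents do not support that: it is a protocol requirement, and the intent-to-treat set (SAP 4.1.1) keeps subjects closed later. A reader might equally take the loss of nearly 12 points at 90 days as the expected cost. The documents give a limit, not a typical delay, and that figure also needs a constant hazard, no screening lead time and every late event counted.

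**Conclusion.** The point holds as an inexpensive improvement. At nominal visit dates the plan observes test subjects d days longer than controls and compares crude proportions, which biases a co-primary estimate against the device. Under the stated assumptions (10% control rate, HR 0.45, 221/443 evaluable, 45 days for all), the shift is about 0.1 to 0.3 points, 0.5 to 1.2 extra test-arm responders, and a power loss of about 1 to 6 points across shape 0.5 to 1 and lead 0 to 180 days. It is smaller if clinical events are already counted only to 24 months after randomization.

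A reader might infer that unequal observation undermines a positive result. It does not: the offset lowers the control-minus-test difference, so it cannot produce a false efficacy claim. Endpoint 1 is timed from randomization in both arms and is unaffected. These statements concern the timing offset alone, not missing MRIs or lesions caused by the procedure.

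**What to change.** 1. In SAP 2.5.1 and 4.3.2, state that 24 months for Endpoint 2 runs from randomization in both arms, including test subjects with no procedure, and count confirmed clinical events only through that common date. Classify MRI lesions as the plan already does, with no rule attributing lesions to particular events in the primary analysis. Report by arm how many subjects had their only follow-up MRI after a clinical event later than day 730, and repeat the test with them classified the other way.
2. Keep the z-test as primary. Prespecify one supporting analysis that uses the actual screening-to-follow-up interval, for example an interval-censored Weibull model reporting the risk difference at day 730 after randomization, repeated with the shape fixed at 0.5 and at 1. Label it supporting only, because it depends on hazard shape. In simulation (4,000 trials per scenario, free shape, 90-day delay, 20% control rate, constant clinical hazard but declining silent hazard) it rejected 0.038 under no effect, above 0.025.
3. Tabulate the screening-to-follow-up MRI interval by arm and the randomization-to-closure delay in the test arm.
4. Reconcile the text of Protocol 3.15 with its Table 7.

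MRI scheduling is unchanged. The cost is SAP text, two tables and one supporting model, using dates in the study records. Only part of the bias in the primary test is removed: step 1 deals with dated clinical events, while lesions seen only on a later MRI still count, and the supporting model corrects the estimate without restoring the primary test's power.

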**Schedule of Test Arm Subject Follow-up and Visit Windows**

Follow-up Visit Interval	Follow-up Visit Interval Window
Early Post-procedure	Typically 4-72 hours post-PFO closure procedure, but must be completed prior to leaving the hospital, out-patient facility, or surgical center
1 month	1 month (30 days) $\pm$ 2 weeks (14 days)
6 months	6 months (182 days) $\pm$ 1 month (30 days)
12 months	12 months (365 days) $\pm$ 2 months (60 days)
18 months	18 months (547 days) $\pm$ 2 months (60 days)
24 months	24 months (730 days) $\pm$ 2 months (60 days)
Year 3	36 months (1,095 days) $\pm$ 2 months (60 days)
Year 4	48 months (1,460 days) $\pm$ 2 months (60 days)
Year 5	60 months (1,825 days) $\pm$ 4 months (120 days)

For Control Arm subjects, all follow-up intervals are calculated from the day of randomization.

